**Adverse Events That are Exempt from Stopping Criteria**

Intrathecal administration of drugs is known to result in untoward effects such as post-lumbar puncture headache, pain, etc. Given the common occurrence of such side-effects following lumbar puncture, it is anticipated that patients may experience AEs temporal to the IT administration procedure which are not attributable to study drug. Therefore, the AE terms listed in [Table 4](#) will be exempted from the assessment of Stopping Criteria:

**Table 4 Adverse Event Preferred Terms Exempted From Stopping Criteria**

Preferred Terms Exempt From Stopping Criteria	
Administration site bruise	Instillation site bruise
Catheter site bruise	Post-lumbar puncture syndrome
Infusion site bruising	Post-procedural discomfort
Infusion site discomfort	Post-procedural contusion
Infusion site pain	Procedural headache
Injection site bruising	Procedural pain
Injection site discomfort	Traumatic lumbar puncture
Injection site pain	

Note: AEs exempted from the Stopping Criteria include the MedDRA PTs listed above and their associated verbatim terms.

While these procedural events are exempt from Stopping Criteria review, they will be recorded as AEs as described in Section 9. In addition, as part of their ongoing review of unblinded safety data, the SMC will carefully review the above-referenced, exempted AE terms to ensure there are no meaningful imbalances between treatment groups.

**4.3.4.2 Multiple-dose Phase Stopping Criteria for an Individual Patient**

Dosing will be stopped for an individual patient if:

1. Patient experiences a serious or intolerable AE that, in the Investigator’s opinion, requires study drug discontinuation.
2. Patient experiences the same related TEAE ≥Grade 3 twice (excepting exempt TEAEs noted in [Table 4](#)).

If a patient meets the individual stopping criteria in the multiple-dose phase, that patient will not receive any more doses of WVE-120101. The patient will be followed up for safety per protocol.

### 4.3.5 Communication of Emergent Safety Concerns

Enrollment to the study will be closely monitored by the Sponsor. If the stopping criteria are met at any point in the study, enrollment and dosing will be suspended for all cohorts until the data are reviewed. Similarly, if an SAE occurs in the sentinel patients in a cohort, no additional patients will be dosed in that cohort until the safety data are reviewed.

All sites will be informed by fax and email if enrollment and/or dosing is suspended. In addition, if enrollment is suspended, the interactive voice/web response system (IXRS) will be adjusted such that no patients can be randomized to treatment or receive additional doses of study drug until the safety review has been completed and a decision has been made to resume enrollment/dosing.

## 5 PATIENT SELECTION AND WITHDRAWAL CRITERIA

Approximately 60 patients will be enrolled. Patients will be assigned to study treatment only if they satisfy all of the inclusion and none of the exclusion criteria. If the patient does not have documented heterozygosity at SNP1, the patient must undergo Prescreening.

At Prescreening, patients will be assessed for eligibility for heterozygosity of the targeted SNP, CAG triplet repeats ( $\geq 36$ ), and presence of the T variant of SNP1 on the same allele as the pathogenic CAG expansion. Patients who do not meet these criteria will be considered Prescreen failures. These results should be recorded for all patients, including those who fail Prescreening.

At Screening, patients who do not meet all remaining inclusion/exclusion criteria will be considered screen failures. The following information should be recorded for all patients who fail screening: demographics, UHDRS Diagnostic Confidence Score, UHDRS TFC score, and reason for screen failure.

### 5.1 INCLUSION CRITERIA

1. Documented ability to understand the written study ICF(s), and has provided signed written informed consent prior to any study procedures.
2. Ambulatory male or female.
3. Age  $\geq 25$  to  $\leq 65$  years old.
4. Body mass index (BMI)  $\leq 32$  kg/m^2.
5. Documented CAG triplet repeats  $\geq 36$  in the *Huntingtin* gene.
6. Documented heterozygosity for SNP1.
7. Documented presence of the T variant of SNP1 on the same allele as the pathogenic CAG expansion
8. Clinical diagnostic motor features of HD, defined as UHDRS Diagnostic Confidence Score = 4.
9. Stage I or Stage II HD, defined as UHDRS TFC scores  $\geq 7$  and  $\leq 13$ .
10. In the opinion of the Investigator, the patient is able to tolerate all study procedures, and is willing to comply with all other protocol requirements.

11. Willingness to practice highly effective contraception for the duration of the study if patients or their partners are of childbearing potential. Non-childbearing potential and highly effective methods of contraception are defined in the protocol ([Section 5.2.1](#)).

## 5.2 EXCLUSION CRITERIA

1. Malignancy or received treatment for malignancy, other than treated basal cell or squamous cell carcinoma of the skin, within the previous 5 years.
2. Positive for Hepatitis B virus (HBV) or Hepatitis C virus (HCV).
3. Known to be positive for human immunodeficiency virus (HIV).
4. Clinically significant medical finding on the physical examination other than HD that, in the judgment of the Investigator, will make the patient unsuitable for participation in and/or completion of the study procedures.
5. Received an investigational drug, including an investigational oligonucleotide, within the past 1 year or 5 half-lives of the drug, whichever is longer.
6. Implantable central nervous system (CNS) device that may interfere with ability to administer study drug via lumbar puncture or undergo MRI scan.
7. Diagnostic and Statistical Manual of Mental Disorders 5th Edition (DSM-5) diagnosis at the Screening Visit of active alcohol, cannabinoid, or other substance use disorder (except nicotine) within 6 months prior to the Screening Visit.
8. Positive for opioids (unprescribed), cocaine, amphetamines, methadone, barbiturates, methamphetamine, or phencyclidine at the Screening Visit.
9. Started or changed dose for concomitant medication for the treatment of HD symptoms or psychiatric disorders within 30 days prior to the Screening Visit (concomitant medications that have been administered on a stable regimen for  $\geq 30$  days are permitted).
10. Pregnant (as determined by a serum pregnancy test) or breast feeding at the Screening Visit, or plans to become pregnant during the course of the study.
11. Clinically significant laboratory abnormality at Screening, including, but not limited to:
  - a Alanine aminotransferase (ALT) or aspartate aminotransferase (AST) values at Screening or Baseline  $>3$  times the upper limit of normal (ULN).
  - b Renal insufficiency, defined as either serum creatinine  $>1.8$  mg/dL or creatinine clearance  $<40$  mL/min.
12. Clinically significant abnormality at Screening electrocardiogram (ECG), including but not necessarily limited to a confirmed QT interval corrected for heart rate (QTc)  $\geq 450$  msec for males or  $\geq 470$  msec for females.
13. Clinically significant cardiovascular, endocrine, hepatic, renal, pulmonary, gastrointestinal, neurologic, malignant, metabolic, psychiatric, or other condition that, in the opinion of the Investigator, precludes the patient's safe participation in the study or would interfere with the study assessments.
14. Bone, spine, bleeding, or other disorder that exposes the patient to risk of injury or unsuccessful lumbar puncture.
15. Inability to undergo brain MRI (with or without sedation).
16. Deemed to be at significant risk for suicidal behavior based on:

- a The opinion of the Investigator; or
  - b Answers “yes” to Actual Suicide Attempts or Suicidal Behaviors in the Suicidal Behaviors section of the Columbia-Suicide Severity Rating Scale (C-SSRS) with reference to a 2-year period prior to the Screening Visit; or
  - c Answers “yes” on any items in the Suicidal Ideation section of the C-SSRS with reference to a 6-month period prior to the Screening Visit; or
  - d Answers “yes” on any items in the Suicidal Ideation section of the C-SSRS at the Baseline Visit since the last visit (Screening Visit).
17. Involved directly or indirectly in the conduct and administration of this study as an Investigator, sub-investigator, study coordinator, or other study staff member, or the patient is a first-degree family member, significant other, or relative residing with one of the above persons involved directly or indirectly in the study.

### **5.2.1 Additional Study Restrictions**

As noted in the inclusion criteria, patients or their partners of childbearing potential must practice true abstinence or use highly effective methods of contraception. True abstinence is defined as refraining from heterosexual intercourse for the duration of the trial. Non-childbearing potential and highly effective methods of contraception are defined in [Section 5.2.1.1](#) and [Section 5.2.1.2](#).

#### **5.2.1.1 Non-Childbearing Potential**

Non-childbearing potential is defined as a female who meets either of the following criteria:

- Postmenopausal state defined as no menses for 12 months without an alternative medical cause, or
- Documented hysterectomy, bilateral tubal ligation, or bilateral oophorectomy.

#### **5.2.1.2 Highly Effective Methods of Contraception**

Contraception methods that can achieve a failure rate of <1% per year when used consistently and correctly are considered highly effective birth control methods. Such methods are defined as 1 of the following:

- True abstinence, defined as refraining from heterosexual intercourse for the duration of the trial, when in line with the preferred and usual lifestyle of the subject.
- Vasectomized partner (if that vasectomized partner is the sole sexual partner and has received medical assessment of the surgical success of the vasectomy).
- An intrauterine hormone-releasing system (IUS).
- Combined (estrogen and progesterone containing) hormonal contraception associated with inhibition of ovulation (oral, intravaginal or transdermal combined).
- Progesterone-only hormonal contraception associated with inhibition of ovulation (oral, injectable, or implantable).
- An intrauterine device (IUD).

**Note that periodic abstinence (calendar, symptothermal, post-ovulation methods), withdrawal (coitus interruptus), spermicides only, and lactational amenorrhea are not acceptable methods of contraception.**

## **5.3 Withdrawal Criteria**

### **5.3.1 Reasons for Withdrawal/Discontinuation**

The duration of the study is defined for each patient as the date a signed written informed consent is provided through the last scheduled follow-up visit or early termination. Patients may withdraw from the study at any time and for any reason without prejudice to their future medical care by the Investigator or at the study site. The reasons for patients not completing the study will be recorded. A patient may be withdrawn from the study for any of the following reasons:

- Serious or intolerable AE that in the Investigator's opinion requires discontinuation of treatment. Patient will be encouraged to remain in the study for safety follow-up.
- A change in the patient's medical condition not consistent with the protocol requirements or that justifies withdrawal.
- Lost to follow-up.
- Pregnancy (refer to [Section 9.5](#)).
- The patient withdraws consent or the Investigator or Sponsor decides to withdraw the from the study.
- Termination of the study by the Sponsor.

Upon occurrence of a serious or intolerable AE, the Investigator will confer with the Sponsor. If a patient is discontinued from the study drug because of an AE, the event will be followed until resolution or until the Investigator and the Sponsor agree that further follow-up is not required.

### **5.3.2 Handling of Withdrawals**

Patients are free to withdraw from the study or study treatment at any time upon request. Patient participation in the study may be stopped at any time at the discretion of the Investigator or at the request of the Sponsor, as described in [Section 5.3.1](#).

Patients who discontinue study treatment or active participation in the study will no longer receive study drug but are encouraged to remain in the study for safety follow-up. When a patient withdraws from the study, the reason(s) for withdrawal will be recorded by the Investigator on the relevant page of the electronic case report form (eCRF). Whenever possible, all patients who discontinue study treatment, or withdraw from the study prematurely, will undergo an early termination visit ([Table 1](#), [Table 2](#), and [Table 3](#)). Patients who fail to return for final assessments will be contacted by the site in an attempt to have them comply with the protocol. At a minimum, 3 documented telephone calls should be made on different days over the course of 2 weeks. If the patient is unreachable by telephone, a registered letter will be sent to the patient requesting him or her to contact the study center. As part of the informed consent, patients will be asked if they are willing to be contacted at the follow-up time point if they have discontinued from study drug or withdrawn from the study.

It is vital to obtain follow-up data on any patient who discontinues study drug or withdraws because of an AE or SAE. In every case, efforts must be made to undertake safety and follow-up procedures as specified by the protocol. All patients who withdraw from the study with an ongoing AE or SAE must be followed until resolution or until the Investigator and the Sponsor agree that further follow-up is not required.

All patients who withdraw from the study due to pregnancy must be followed to record the outcome of the pregnancy.

### 5.3.3 Replacements

Patients who drop out before Day 28 (2, 4, 8, and 16 mg cohorts) or Day 14 (32 mg cohort) in the single-dose phase will be replaced in accordance with the requirements for dose escalation. Patients who drop out after this point may be replaced with patients directly entering the multidose part of the study.

## 6 STUDY TREATMENTS

### 6.1 METHOD OF ASSIGNING PATIENTS TO STUDY DRUG

Patients who meet all of the inclusion criteria and none of exclusion criteria will be randomized into the study on Day 1 to receive either active study drug or placebo, both administered intrathecally. Patients will receive WVE-120101 (9 patients in each cohort) or placebo (3 patients in each cohort).

In order to allow for evaluation of a full multidose cohort (N=12), new patients may be enrolled directly in the multiple-dose portion to account for those patients who do not roll over from the single-dose portion to the multi-dose portion. Treatment assignment will be performed such that these treatment-naïve patients will receive the same treatment as the patient who completed the single-dose portion.

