## **4 STUDY DESIGN**

### **4.1 STUDY DESIGN OVERVIEW**

This is a Phase 1b/2a multicenter, randomized, double-blind, placebo-controlled study to evaluate the safety, tolerability, PK, and PD of IT WVE-120101 in adult patients with early manifest HD who carry a targeted single nucleotide polymorphism, SNP1.

This study will evaluate a single dose of WVE-120101 followed by multiple doses in eligible patients with early manifest HD. To participate in the study, patients must have documented heterozygosity for SNP1 with the thymine (T) variant on the same allele as the CAG triplet expansion. Patients who have not previously undergone SNP analysis will be required to be prescreened to determine heterozygosity for SNP1. The prescreening assessment will have a separate informed consent form (ICF).

Patients may participate in the complete study, in which they will receive all 4 doses. In order to allow for evaluation of a full multi-dose cohort (N=12), new patients may be enrolled directly in the multiple-dose portion to account for those patients who do not roll over from the single-dose portion to the multi-dose portion. These patients will receive 3 doses. Five dose cohorts will be evaluated (2, 4, 8, 16, and 32 mg).

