## **4.2 SCHEDULE OF ASSESSMENTS**

The schedule of assessments for patients participating in the single and multiple dose portions of the study is presented in [Table 1](#) (2, 4, 8, and 16 mg cohorts) and [Table 2](#) (32 mg cohort). The Schedule of Assessments for patients participating in the multiple-dose portion of the study only is presented in [Table 3](#).

**At each relevant time point, the UHDRS, PBA-s, and Columbia-Suicide Severity Rating Scale (C-SSRS) should be performed prior to other assessments.**

**Table 1 Schedule of Assessments for Patients Participating in Both the Single and Multiple Dose Portions of the Study (2, 4, 8, and 16 mg cohorts)**

Visit	Pre-Screening a	Screening b	Double-Blind Treatment (Single Dose)		Sentinel Patient Follow-up	Follow-up		Double-Blind Treatment (Multiple Dose)			Follow-up		
	1	2	3	4	5	6	7	8 c	9	10	11 or ET	12	13
Week		-4 to 0	0	0	0	2	4	8	12	16	20	28	30
Study Day (Visit Window, if applicable) Event/Assessment		Day -28 to -1	Day -6 to Day 1 (Baseline)	Day 2 (24 ± 4h postdose)	Day 3 (48 ± 4h postdose)	Day 14 (±2)	Day 28 (±3)	Day 56 (±3)	Day 84 (±3)	Day 112 (±3)	Day 140 or ET (±5)	Day 196 (±5)	Day 210 d (EOS) (±5)
Predose/Non-dosing Days													
Patient informed consent form (ICF) Signed	X	X											
Inclusion/exclusion criteria		X	X					X					
Medical history and demographics		X											
Physical examination e		X	X	X	X	X	X	X	X	X	X	X	
C-SSRS f		X	X*			X	X	X*	X*	X	X*		
UHDRS		X	X			X	X	X	X	X	X		
PBA-s		X	X			X	X	X	X	X	X		
Drug screen g		X											
Urine pregnancy test h			X*					X*	X*	X*			
Adverse event monitoring		X	X*	X q	X q	X	X	X*	X*	X*	X	X	X
Prior and concomitant medications		X	X*	X q	X q	X	X	X*	X*	X*	X	X	X
3T MRI of the brain (without contrast)		X					X				X		
Vital signs i		X	X*	X	X	X	X	X*	X*	X*	X	X	
12-lead ECG j		X					X						
Serum pregnancy test h		X											
Clinical laboratory tests k		X	X	X	X	X	X	X	X	X	X	X	
Hepatitis (HBsAg, HCV)		X											
Blood sample for Prescreening assays l	X												
Blood sample for PK m			X	X	X	X	X	X	X	X	X		
Blood sample for immunogenicity n			X				X	X	X	X	X	X	
CSF sample for safety, exposure, and PD o			X*				X	X*	X*	X*	X r	X	
Randomization			X										

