**Table 3 Schedule of Assessments for Treatment-Naïve Patients in the Multiple-Dose Portion of the Study**

Visit	Pre-Screening a	Screening b	Double-Blind Treatment (Multiple Dose)			Follow-up		
	1	2	8 (7 g )	9 (8 g )	10 (9 g )	11 (10 g ) or ET	12 (11 g )	13 (12 g )
Week		-4 to 0	8 (4 g )	12 (8 g )	16 (12 g )	20 (16 g )	28 (24 g )	30 (26 g )
Study Day (Visit Window, if applicable) Event/Assessment		Day -28 to -1	Day 56 (28 g ) (±3) (Baseline)	Day 84 (56 g ) (±3)	Day 112 (84 g ) (±3)	Day 140 (112 g ) or ET (±5)	Day 196 (168 g ) (±5)	Day 210 e (182 g ) (EOS) (±5)
Predose/Non-dosing Days								
Patient informed consent form (ICF) Signed	X	X						
Inclusion/exclusion criteria		X	X					
Medical history and demographics		X						
Physical examination d		X	X	X	X	X	X	
C-SSRS c		X	X*	X*	X	X*		
UHDRS		X	X	X	X	X		
PBA-s		X	X	X	X	X		
Drug screen f		X						
Urine pregnancy test e			X*	X*	X*			
Adverse event monitoring		X	X*	X*	X*	X	X	X
Prior and concomitant medications		X	X*	X*	X*	X	X	X
3T MRI of the brain (without contrast)		X				X		
Vital signs h		X	X*	X*	X*	X	X	
12-lead ECG i		X						
Serum pregnancy test e		X						
Clinical laboratory tests j		X	X	X	X	X	X	
Hepatitis (HBsAg, HCV)		X						
Blood sample for Prescreening assays k	X							
Blood sample for PK l			X	X	X	X		
Blood sample for immunogenicity m			X	X	X	X	X	
CSF sample for safety, exposure, and PD n			X*	X*	X*	X p	X	
Treatment Assignment								
Study drug administration via IT injection o			X	X	X			
Postdose on Dosing Days								
Physical examination d			X	X	X			
Adverse event monitoring			X	X	X			

	Pre-Screening a	Screening b	Double-Blind Treatment (Multiple Dose)			Follow-up		
Visit	1	2	8 (7 a )	9 (8 a )	10 (9 a )	11 (10 a ) or ET	12 (11 a )	13 (12 a )
Week		-4 to 0	8 (4 a )	12 (8 a )	16 (12 a )	20 (16 a )	28 (24 a )	30 (26 a )

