Study Day (Visit Window, if applicable) Event/Assessment		Day -28 to -1	Day 56 (28 a ) (±3) (Baseline)	Day 84 (56 a ) (±3)	Day 112 (84 a ) (±3)	Day 140 (112 a ) or ET (±5)	Day 196 (168 a ) (±5)	Day 210 c (182 a ) (EOS) (±5)
Clinical laboratory tests d			X	X	X			
Concomitant medications			X	X	X			
Vital signs h			X	X	X			
Blood samples for PK i					X			
Study completion								X

Abbreviations: AE = adverse event; CAG = cytosine-adenine-guanine; CSF = cerebrospinal fluid; C-SSRS = Columbia-Suicide Severity Rating Scale; ECG = electrocardiogram; EOS = end of study; ET = early termination; h = hour; HBsAg = hepatitis B surface antigen; HCV = hepatitis C virus; ICF = informed consent form; IT = intrathecal; MRI = magnetic resonance imaging; PBA-s = Short Problem Behaviors Assessment; PD = pharmacodynamics; PK = pharmacokinetics; SNP= single nucleotide polymorphism; SNP1 = SNP rs362307; T= thymine; UHDRS = Unified Huntington’s Disease Rating Scale.

Note: The UHDRS, PBA-s, and C-SSRS should be completed prior to any other assessments. Assessments completed predose on Day 56 (Day 28 for the 32 mg cohort) are considered Baseline.

Patients who are treatment-naïve for the multiple-dose portion of the study will undergo Prescreening and Screening, and then receive their first dose on Day 56 (Visit 56).

**\*For each dosing visit during the multiple dose phase, these predose procedures must be performed predose on the day of dosing. All other predose assessments (inclusion/exclusion criteria [Day 56/Visit 8 for 2, 4, 8, and 16 mg cohorts or Day 28/Visit 7 for 32 mg cohort], physical examination, UHDRS, PBA-S, clinical laboratory tests [including a blood sample to confirm platelet count and prothrombin clotting time], blood sample for PK, and blood sample for immunogenicity) may be performed up to a week prior to dosing.**

- a Prescreening is only required for patients who do not have documented heterozygosity for SNP rs362307 (SNP1) with the T variant on the same allele as the cytosine-adenine-guanine (CAG) triplet expansion. Prescreening can happen anytime before Screening. It is anticipated that it will take at least 6 weeks to process the results of this testing.
- b Screening assessments can occur on multiple days, provided they are within the 4-week Screening period.

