## 10.3 STUDY PATIENTS

### 10.3.1 Analysis Populations

The following study populations will be evaluated:

- Safety population will include all randomly assigned patients who receive at least 1 dose of WVE-120101.
- PD population will include all patients in the safety population who have at least 1 postbaseline CSF sample.
- PK population will include all patients in the safety population who have sufficient plasma or CSF concentration data, as determined by the pharmacokineticist, for inclusion in the descriptive statistical analysis.
- Per Protocol Population will include all patients in the Safety population who have no major protocol deviations.

The Safety population will be used for the safety analysis, demographics, and other baseline patient characteristics; the PD population will be used for the PD analysis; the PK population will be used for the PK analysis; and the Per Protocol population will be used for all analyses of clinical effects.

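### Patients who enter the multiple-dose portion directly are matched to an earlier patient's treatment, yet the Safety population and the three sets nested in it admit only randomly assigned patients

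*Combined protocol and SAP*

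**What the plan says.** Section 4.1 states that "new patients may be enrolled directly in the multiple-dose portion to account for those patients who do not roll over" from the single-dose portion, so that a full multiple-dose cohort of 12 can be evaluated. Section 5.3.3 adds that patients lost after Day 28 (Day 14 in the 32 mg cohort) may be replaced by such direct entrants.

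Section 6.1 gives two assignment rules. Eligible patients "will be randomized into the study on Day 1 to receive either active study drug or placebo, both administered intrathecally", 9 active and 3 placebo per cohort. For direct entrants: "Treatment assignment will be performed such that these treatment-naïve patients will receive the same treatment as the patient who completed the single-dose portion".

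Tables 1 and 2, for patients in both portions, carry a row headed "Randomization". Table 3, for direct entrants, has "Treatment Assignment" instead. Its notes say that these patients "will undergo Prescreening and Screening, and then receive their first dose on Day 56" (Day 28 at 32 mg).

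Section 10.3.1 reads: "Safety population will include all randomly assigned patients who receive at least 1 dose of WVE-120101". The PD, PK and Per Protocol populations are each defined as members of the Safety population who meet a further condition.

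**The concern.** The first condition in the Safety definition is random assignment, and the plan describes no random draw for direct entrants. Because the other three sets are nested in Safety, failing that condition removes a patient from all four. Safety and tolerability are the primary endpoint. CSF mHTT is analysed in the PD population, and TFC and the other clinical effects in the Per Protocol population. The summaries at risk are therefore the ones that the direct entrants were brought in to complete.

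The problem is separate from the requirement, in the same sentence, of a dose of WVE-120101, which taken literally excludes placebo patients. Changing that phrase to cover placebo would leave the random-assignment condition in place, and direct entrants would still be outside.

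**Working it through.** **1. The texts side by side**

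| Item | Single-dose entrants | Direct multiple-dose entrants |
|---|---|---|
| Assignment (6.1) | Randomised on Day 1 | Same treatment as an earlier single-dose patient |
| First dose | Day 1 | Day 56 (Day 28 at 32 mg) |
| Schedule row | "Randomization" (Tables 1 and 2) | "Treatment Assignment" (Table 3) |
| Meets the random-assignment condition of 10.3.1 | Yes | Not on the wording given |

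If k direct entrants bring a multiple-dose cohort up to 12, at most 12 − k of its patients satisfy that condition. Nothing in the supplied text counts direct entrants as randomised or adds them to a set.

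Two other parts of Section 10 also overlook them. Section 10.3.2 bases disposition on randomised patients. Section 10.5 takes PD baseline at Day 1, whereas Table 3 puts these patients' baseline at Day 56 or Day 28. This looks like a gap in drafting rather than one loose word.

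**2. Size, by illustration**

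Planned total: 5 cohorts × (9 + 3) = 60, which agrees with the approximately 60 stated.

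The only precision figure is in Section 10.2: ±110 fM, two-sided 90%, 9 patients per active dose. The SD comes from a cited source and is not in the documents, so the figure cannot be reproduced independently. I read ±110 as a half-width and solved for the SD.

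- Formula: half-width = t(0.95, n − 1) × SD / √n
- SD = 110 × √9 / t(0.95, 8) = 330 / 1.860 ≈ 177 fM
- With the normal quantile instead: 330 / 1.645 ≈ 201 fM

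Let k of the 9 active places be held by direct entrants who are left out (k is assumed):

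| k | n | Half-width, t (fM) | Half-width, normal (fM) |
|---|---|---|---|
| 0 | 9 | ±110 | ±110 |
| 1 | 8 | ±119 | ±117 |
| 2 | 7 | ±130 | ±125 |
| 3 | 6 | ±146 | ±135 |

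For example, k = 3 gives 2.015 × 177.46 / √6 ≈ 146.

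These figures apply to mHTT summaries at multiple-dose visits. A patient who did not roll over may still contribute a postbaseline sample from the single-dose period.

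**The case against.** The best counter-argument is that a direct entrant inherits a place whose treatment was fixed by the 3:1 randomisation, and so is randomly assigned at one remove. The stated aim of a full cohort of 12 makes deliberate exclusion implausible. The Table 3 row label proves little alone, since Section 7.1 uses the same term for what the randomisation scheme produces. A separate SAP, to which the protocol defers details, might also settle the matter.

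Part of this stands: inclusion was very probably intended. But the inherited-place reading is written nowhere, and Section 6.1 ties randomisation to a Day 1 that these patients lack. Two programmers could build different Safety sets and each cite Section 10.3.1. No separate SAP text is supplied, and a different definition there would still conflict with the protocol's.

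A reader might infer more than the documents support:

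- **That every replacement is excluded.** Under Section 5.3.3, patients lost before Day 28 (Day 14 at 32 mg) are replaced to meet the requirements for dose escalation. Those replacements belong to the single-dose phase, where randomisation applies.
- **That the data are lost.** Section 10.9.1 lists all AEs and SAEs by patient, and Section 10.6 analyses immunogenicity in all patients. The summaries are at risk, not the record.
- **That matching reveals treatment at the site.** No section says that a site learns whose place is being filled. Under Section 7.1 assignment notices go to designated pharmacy personnel and site staff stay blinded.
- **That a head-count can be given.** The documents state no non-roll-over rate, and on the same literal reading placebo entrants are already excluded by the WVE-120101 wording.

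**Conclusion.** The point holds as a defect in a stated rule. Taken at its word, Section 10.3.1 leaves direct multiple-dose entrants out of the Safety, PD, PK and Per Protocol summaries, contrary to the purpose for which Sections 4.1 and 6.1 enrol them. It should be corrected before the analysis sets are built.

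Its size depends on how many direct entrants there are, which the documents do not say. If 2 or 3 of 9 active places in a cohort were affected, the mHTT half-width would grow from ±110 fM to about ±130 or ±146 fM by the t calculation (±125 or ±135 by the normal one). Those figures rest on the assumed number of places, on reading ±110 as a half-width, and on an SD solved from it. The textual conclusion depends on none of these.

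Section 6.1 leaves a related ambiguity. It matches the entrant to a patient who completed the single-dose portion, whereas Section 5.3.3 also allows replacement of someone who left after Day 28 or Day 14 without completing it. Whose treatment then applies is not clear.

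**What to change.** In Section 10.3.1, define the Safety population as all patients who receive at least one dose of study treatment (WVE-120101 or placebo), whether randomised or assigned as direct multiple-dose entrants, analysed by treatment received. The PD, PK and Per Protocol definitions then follow unchanged. The same sentence also repairs the separate omission of placebo patients.

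Flag direct entrants in the analysis data set and in the listings, so that patients who were not individually randomised can be identified. A summary without them is optional, since the analyses are descriptive. Check the disposition counts in Section 10.3.2 and the Day 1 baseline in Section 10.5 against the new wording.

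The cost is one revised definition and one flag variable. Neither the sample size nor the assignment system needs to change.
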